8.3. Subject Discontinuation/Withdrawal from the Study

Subjects are free to withdraw from participation in the study at any time upon request.

An investigator may discontinue or withdraw a subject from the study for any reason, including the following:

- Pregnancy
- Significant study noncompliance
- If any clinical AE, laboratory abnormality, or other medical condition or situation occurs such that continued participation in the study would not be in the best interest of the subject
- If the subject meets an exclusion criterion (either newly developed or not previously recognized) that precludes further study participation

The reason for participant discontinuation or withdrawal from the study will be recorded on the eCRF.

Whenever possible and reasonable, the evaluations that were to be conducted at the completion of the study should be performed at the time of early discontinuation.

The following actions must be taken if a subject fails to return to the clinic for a required study visit:

- The site will attempt to contact the subject and reschedule the missed visit the following business day, as well as counsel the subject on the importance of maintaining the assigned visit schedule
- Before a subject is deemed lost to follow-up, a member of the study team will make every effort to regain contact with the subject (where possible, 3 telephone calls and, if necessary,

a certified letter to the subject's last known mailing address or local equivalent methods). These contact attempts should be documented in the subject's medical record or study file.

- Should the subject continue to be unreachable, he or she will be considered to have withdrawn from the study with a primary reason of lost to follow-up.

Subjects who are unable to attend the End of Study Visit will be contacted by telephone for reporting of AEs.

8.4. Subject Replacement Criteria

Subjects who withdraw consent, are withdrawn, or discontinue from the study may be replaced.

[figure not shown]
Randomized subjects withdrawn from the study may not re-enter. The subject number for a withdrawn subject will not be reassigned to another subject.

9. TREATMENTS

9.1. Identification of Investigational Product(s)

SB-121 is a preparation of *L. reuteri* with Sephadex® and maltose.

L. reuteri is a Gram-positive nonsporulating facultative anaerobic bacteria and the strain utilized in SB-121 is *L. reuteri* ATCC 23272, grown in De Man, Rogosa and Sharpe (MRS) broth and lyophilized in the presence of cryoprotectants (sorbitol and maltodextrin).

The Daily Medication Instructions will detail the steps for storage, preparation and consumption of the IP.

9.1.1 Rescue Medication

Not applicable.

9.2. Selection of Timing of Dose for Each Subject

This is a daily-dose study. The first dose of SB-121 or placebo will be administered at the study site, according to the treatment group to which the subjects are allocated, on the morning of the Day 1 and after confirmation that the subject remains eligible.

Starting on Day 2, the daily dose of study medication is to be taken by mouth (consumed orally), in a single sitting at home. The study medication should only be taken once a day by the study subject. If at all possible, the study medication should be taken at the same time every day (for example, every day around breakfast).

9.3. Dose Adjustment Criteria

Dose adjustment is not allowed in this study.

9.3.1 Stopping Rules

The clinical severity of an AE will be graded according to the NCI-CTCAE (version 5.0, 27-Nov-2017). If an NCI-CTCAE scale is not available for a given AE. Refer to Section 11.2.2.1. The trial will be stopped in the event of ≥ 1 subject reporting a Grade 4 laboratory and/or clinical AE considered related to SB-121 or ≥ 2 subjects reporting Grade 3 laboratory and/or clinical AE considered related to SB-121.

9.4. Treatment Compliance

All subjects will receive the first dose of IP at the study site under the supervision of appropriate study personnel. Administration details and IP batch or lot number(s) will be recorded in the subject's eCRF. Information regarding subsequent doses is to be recorded in the Patient Diary and returned to the study site.

9.5. Study Blind

This is a double-blind, placebo-controlled cross-over study. The study team and subjects will be blinded to the randomized study treatment assignments. The study blind will be maintained throughout the duration of the clinical trial. Only the dispensing pharmacist will be aware of study drug assignment.

9.6. Procedure for Breaking the Study Blind

In a medical emergency where knowledge of the subject's treatment assignment may influence the subject's clinical care, the investigator may access the subject's treatment assignment. Under these circumstances, the investigator will contact the un-blinded pharmacist to get the subject's treatment assignment. Emergency unblinding can thus be made for any subject without affecting the double-blind nature of the study. The Medical Monitor will be notified of any emergency unblinding requests. The investigator should make every effort to discuss the rationale for emergency unblinding with the Medical Monitor prior to unblinding the individual subject. Once a subject is unblinded, he/she must be withdrawn from the study. The subject's treatment assignment should not be shared with the sponsor/designee and other study team members. The investigator must record the reason for the emergency unblinding in the source documents and record it in the electronic database.

9.7. Permitted and Prohibited Therapies

All concomitant medications used (including over-the-counter medications and herbal supplements) will be recorded in the source document and on the appropriate eCRF. Information on prior and concomitant medications will be collected at Screening; any changes to concomitant medications will be reported at each subsequent study visit.

Medications that started prior to treatment will be considered prior medications whether or not they were stopped prior to treatment. Any medications continuing or starting post-treatment will be considered to be concomitant. If a medication starts prior to treatment and continues after treatment with IP is started, it will be considered both prior and concomitant.

9.7.1 Prohibited Therapies

The following therapies are prohibited both before and during the study:

- Proton pump inhibitor within 2 weeks prior to screening
- Use of systemic antibiotics within 2-weeks prior to Screening
- Use of supplemental probiotics within 2 weeks prior to screening except for yogurt
- Current use of immunosuppressive medications, including corticosteroids
- Monoclonal antibodies (e.g., adalimumab) within 4-weeks of screening

- Any IP (or investigational device) within 30 days before enrollment in this study.

For subjects receiving excluded therapies after randomization, eligibility for study continuation, will be determined on a case-by-case basis at the discretion of the medical monitor.

9.7.2 Permitted Therapies

Other concomitant medications (i.e., those not listed as prohibited in Section 9.7.1) are allowed, but should be limited to those medications considered necessary in the investigator's judgment. Subjects can continue on stable doses of their medications for AD and associated symptoms, as determined by the investigator.

9.8. Dispensing and Storage

The investigator must confirm the receipt of the IP with his or her signature. The investigator must keep a copy of this receipt and another copy will be stored at Scioto Biosciences Inc.

9.9. Drug Accountability

The investigator must maintain adequate records showing the receipt, dispensing, return, or other disposition of the IP, including the date, quantity, batch or code number, and identification of subjects (subject number) who received the IP. The IP may not be relabeled or reassigned for use by other subjects. If any of the IP are not dispensed, are lost, stolen, spilled, unusable, or are received in a damaged container, this information must be documented and reported to the sponsor.

9.10. Labeling and Packaging

9.10.1 Labeling

[figure not shown]
The IP will be provided as a kit, with a label affixed that meets the applicable regulatory requirements and may include the following:

- Protocol number
- Unique kit identifier
- Subject number (record at the time of dispensing)
- Manufacture and expiry date
- Package contents
- Storage instructions
- Caution: "New Drug – Limited by United States Law to Investigational Use" and "Keep out of reach of children"
- Sponsor name and address

Other information may be included as required.

All empty packaging or packaging containing unused SB-121 components should be saved for final disposition by the sponsor or designee.

9.10.2 Packaging

10. STUDY PROCEDURES

Written informed consent must be obtained before any study-related procedures are initiated, including the cessation of prohibited concomitant therapy.

For the timing of assessments and procedures throughout the study, refer to the Schedule of Events (Section 2.2). Throughout the study, every reasonable effort should be made by study personnel to follow the timing of assessments and procedures in the Schedule of Events for each subject. If a subject misses a study visit for any reason, the visit should be rescheduled as soon as possible.

10.1. Study Duration

The overall study duration is expected to be approximately 14-weeks.

The planned sequence and duration of the study periods will be as follows:

1. Screening: Up to 14 days
2. Study Period 1: 28 days
3. 14-day washout period
4. Study Period 2: 28 days
5. Post-treatment: Up to 14 days

The maximum study duration for each subject is approximately 98 days.

10.2. Study Periods and Visits

10.2.1 Screening

The subject will be screened within 14 days before randomization in the study. After informed consent, the following procedures will be performed at screening:

Medical and Psychiatric History: A medical and psychiatric history will be completed by a member of the study team to assess that the subject meets study eligibility criteria. The following will be part of this:

1. Autism Diagnostic Observation Schedule - 2 (ADOS-2) Modules 2, 3 or 4 (Lord 2000, Lord 1989). The ADOS-2 is an investigator-based AD diagnostic assessment that places the participant in naturalistic situations demanding specific social and communication responses. It covers social communication, social relatedness, play, and repetitive behaviors. Participants who are able to complete Modules 2, 3 or 4 will be enrolled in the study. Modules 2, 3 and 4 of the ADOS were chosen for this project to accommodate the age range in this study. Additionally, they accommodate verbal skills such as sentence speech and phrase speech. Furthermore, these modules assess individuals' ability to report on an event through several opportunities (e.g., description of a picture). This information will be vital in assessment of participants' ability to report adverse events.

2. **DSM-5 Checklist:** A DSM-5 checklist will be completed by a member of the study team conducting the diagnostic assessment. The checklist includes a listing of the current symptom criteria for AD in the DSM-5 (American Psychiatric Association 2013).

Concomitant medications will be recorded.

Physical Examination: A study physician or other qualified study team member will complete a general physical examination to assess that the subject meets study eligibility criteria. This includes checking the vital signs (pulse, BP and oral temperature) and height and weight.

Screening Labs: Blood samples for hematology and chemistry will be collected. A urine sample will be collected for urine analysis from all subjects, and a urine sample will be collected from females of child bearing potential for a pregnancy test.

Eligible subjects will be provided with a stool sampling kit to collect a pretreatment stool sample within approximately 48 hours before receiving the first dose of IP.

Rescreening: Rescreening of a subject may be allowed once under circumstances where the subject passed the screening but could not be randomized within the 14-day screening window due to logistical, personal or other unforeseeable reasons. For rescreening in these circumstances, all screening measures will be repeated with the exception of the DSM and ADOS-2.

10.2.2 Post-screening

A pretreatment stool sample within approximately 48 hours before receiving the first dose of the IP.

For all eligible subjects the following tests will be performed by a study team member as indicated in the Schedule of Events (Section 2.2):

10.2.2.1 Autism Pathophysiology Measures

Wechsler Abbreviated Scale of Intelligence Scale-Second Edition (WASI-II): The WASI-II (Wechsler 2017) is a tool used to evaluate an individual's cognitive functioning and generate IQ scores. There are 4 subtests: Block Design, Vocabulary Matrix, Reasoning, and Similarities. This measure will only be done at baseline, prior to the first dose.

Social Communication Questionnaire (SCQ): The SCQ, originally called the Autism Screening Questionnaire, is a continuous measure of AD behaviors and symptoms based on the Autism Diagnostic Interview- Revised (ADI-R) (Johnson 2011, Chandler 2007). This measure will only be done at baseline, prior to the first dose.

Clinical Global Impressions Severity (CGI-S) and Improvement (CGI-I) Subscales: The clinician-rated CGI-S is rated on a 7 point Likert scale from minimally to the most severely affected, anchored to core symptoms of AD. Clinical response to drug exposure will be assessed with the clinician-rated CGI-I (Guy 1976). The CGI-I is a 7-point scale designed to measure symptomatic change that compares the patient's clinical condition to the baseline. The CGI-I assessment will focus on the core symptoms of AD. CGI-I is a gold standard measure of potential change with treatment in placebo-controlled pharmacotherapy trials in AD.

Vineland Adaptive Behavior Scales (3rd edition): The VinelandTM-3 measures communication, daily living skills and socialization skills. The VinelandTM-3 will be administered to a subject's reliable caregiver in this study, during which the rater from the study team will ask the caregiver open ended questions relating to the subject's activities and behavior.

Aberrant Behavior Checklist (ABC): The ABC is an informant-based questionnaire consisting of 58 items subdivided amongst 5 scales: irritability, lethargy and social withdrawal, stereotypic behavior, hyperactivity/non-compliance, and inappropriate speech (Aman 1985). A score for each item ranges from 0 indicating "no problem" to 3 indicating "severe problem". Scale scores are calculated by summing the items within that scale. Higher scores indicate greater impairment.

Woodcock Johnson 3rd Edition (WJ-III): The Spatial Relations and Auditory Attention subtests of the WJ-III will be administered. The Spatial Relations subtest will assess the visual spatial thinking domain with a task that requires the identification of parts needed to form a complete shape. Responses can be oral or motoric (pointing). The Auditory Attention subtest will assess auditory processing (speech/sound discrimination) requiring the identification of orally presented words amid increasingly intense background noise. Examinees point to a picture of the word presented.

Repeatable Battery for Assessment of Neuropsychological Status (RBANS): The RBANS is a neuropsychological battery for persons with neurological disorders. The RBANS covers five domains including Immediate Memory, Language, Attention, Visuospatial/Constructional, and Delayed Memory (Randolph 1998).

Test of Attentional Performance for Children (KiTap): The KiTap is an automated computer based assessment of attentional performance developed and normed for the pediatric population. Despite its development in pediatrics, the KiTap is well suited for use in developmental disabilities across all age ranges and has been normed specifically in FXS in adults and youth (Knox 2012). The task presents an enchanted castle animation and investigates performance in a number of areas including Alertness, Vigilance, Visual Scanning, Distractibility, Attention, Flexibility, and Sustained Attention.

EEG Measures: Subjects will complete EEG evaluations prior to the first dose of IP (baseline) and following four weeks of chronic dosing in each treatment period. The procedure will be performed on all subjects but inability to complete the procedure will not be considered a deviation.

The EEG tests include:

1. EEG resting state task: Participants will complete a 5-minute resting state EEG protocol.
2. Auditory habituation Evoked Response Potential (ERP): ERPs will be recorded during passive listening.
3. Chirp modulated sweep: Subjects will passively listen to auditory stimuli consisting of a amplitude modulated chirps.

Eye Tracking/Pupillometry Measures: Infrared eye tracking will be used as a measure of eye gaze and pupillary reactivity in response to visual processing of human faces and of social scenes at prior to the first dose of IP (baseline) and following four weeks of chronic dosing in each treatment period.

10.2.2.2 Stool Sampling

Following screening, all subjects who meet eligibility criteria, will be provided with sample kits comprising a commode specimen collection system with closed container storage, biohazard bags, and with labels for the sample containers, which subjects should complete with the time and date that the sample was obtained. Styrofoam coolers with ice-packs will be provided to subjects to keep samples cool during transport. Instructions for stool collection and shipping will be provided.

Stool samples will be collected for determination of the presence of Sephadex® microspheres. The stool samples will also be used for the evaluations of potential biomarkers of inflammation, based on changes from baseline (pre-treatment).

Subjects will be instructed to collect a total of 5 stool samples at home according to the following schedule:

- A pretreatment stool sample within approximately 48 hours before receiving the first dose of the IP.
- Post-treatment samples:
 - Sample 1 should be taken no sooner than 21 days or later than 28 days into the first treatment period of the study (prior to the completion of the first treatment period)
 - Sample 2 should be taken approximately 7 days into the wash-out period after the first treatment period of the study and before the second treatment period
 - Sample 3 should be taken no sooner than 21 days or later than 28 days into the second treatment period of the study (prior to the completion of the second treatment period)
 - Sample 4 should be taken approximately 7 days after the completion of the second treatment period of the study

10.2.2.3 Sampling

Samples for changes from baseline will be collected for the evaluation of the following systemic biomarkers: Plasma oxytocin, plasma vasopressin, serum hs-CRP, tumor necrosis factor- α , and stool biomarkers.

10.2.3 Treatment Visit – Day 1 (See Schedule of Events Section 2.2)

Following confirmation of eligibility criteria, subjects will be randomized to receive SB-121 or placebo. Subjects will undergo study-specific procedures on Day 1 in accordance with the Schedule of Events.

Following baseline tests, all subjects will be given their first dose of either SB-121 or placebo at the clinic. The IP will be prepared according to the provided Daily Medication Instructions.

All subjects receive an additional 27 doses of IP to be self-administered once daily at home at about the same time every day (e.g. around breakfast). In addition to the 27 oral doses, additional material will be provided for use in the event of spillage. Refer to the Daily Medication Instructions

for details on IP storage, reconstitution and consumption. All subjects will be instructed to capture the date and time of each dose of IP on the Patient Diary.

Subjects will be discharged after all Day 1 evaluations have been completed.

10.2.4 Follow-up Visits (See Schedule of Events – Section 2.2)

Follow-up clinic visits will be conducted on Day 28, Day 1 of treatment period 2 and Day 28 of treatment period 2. Subjects will undergo study-specific procedures in accordance with the Schedule of Events.

Telephone Calls: Weekly telephone calls will be conducted by a member of the study team between in person visits during each treatment period in accordance to the Schedule of Events. These calls will be to assess IP compliance and to capture any adverse events. If a concerning adverse event is identified during a phone call, the study staff will consult with the investigator and an unscheduled in-person study visit and/or lab work may be added.

10.2.5 End of Study / Early Termination

An End-of-Study Visit will be conducted on Day 28 of Study Period 2. Subjects will undergo study-specific procedures in accordance with the Schedule of Events.

Subjects who discontinue the study early for any reason will be asked to attend the study site for an Early Termination (ET) Visit; procedures performed at the ET visit will be the same as those conducted for subjects attending the End-of-Study Visit.

Subjects who are unable to attend the End of Study Visit/Early Termination Visit will be contacted by telephone for reporting of AEs. However, investigators should make every effort to ensure that subjects do attend.

The Post-Treatment Period will last up to 14 days, wherein subjects will not receive any study drug. During this time, subjects will be contacted by telephone for reporting of AEs. A post treatment stool sample is to be collected approximately 7 days after the completion of the second treatment period of the study

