 - Sample 2 should be taken approximately 7 days into the wash-out period after the first treatment period of the study and before the second treatment period
 - Sample 3 should be taken no sooner than 21 days or later than 28 days into the second treatment period of the study (prior to the completion of the second treatment period)
 - Sample 4 should be taken approximately 7 days after the completion of the second treatment period of the study

Subjects will be advised to contact the study site immediately in the event of symptoms consistent with bacteremia (e.g., fever, chills, diaphoresis) to obtain appropriate medical care as indicated. In the event that subjects develop symptoms consistent with bacteremia, 2 blood samples will be collected, when feasible for blood cultures, and microbial identification.

Follow-up visits will be conducted on Day 28 of treatment period 1, Day 1 of treatment period 2 and Day 28 of treatment period 2 as per the Schedule of Events.

Details of AEs occurring throughout the study will be captured at each visit, additionally AEs of special interest will be captured in the Patient Diary. Weekly telephone calls will be conducted by the study team between in person visits during each treatment period. These calls will record and evaluate adverse events and will also determine IP compliance. In the case of adverse events identified during a phone call, the study team may determine that an unscheduled in-person study visit and/or lab tests may be required. Gastrointestinal events (nausea, vomiting, diarrhea, constipation, abdominal distention, abdominal pain/cramps, and flatulence) and systemic events (fever, chills, diaphoresis) occurring at any time during the study and within 2 weeks after the last dose of IP will be considered AEs of special interest (AESIs), and will be solicited.

The investigational product will be provided to subjects in 2 bottles, the contents of which will be combined, allowed to sit for a period of 15-45 minutes at room temperature, then combined with a predefined drink for consumption. See the Daily Medication Instructions for additional details.

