10.2.6.1 Adverse Events

The definitions and management of AEs, and any special considerations for AEs, are provided in Section 11.

Details of AEs occurring throughout the study will be collected by a member of the study team at each visit. Weekly telephone calls will be conducted by a member of the study team between in person visits during each treatment period. These calls will record and evaluate AEs and will also determine IP compliance. In the case of adverse events identified during a phone call, the investigator or designee may determine that an unscheduled in-person study visit and/or lab tests may be required. Gastrointestinal events (nausea, vomiting, diarrhea, constipation, abdominal distention, abdominal pain/cramps, and flatulence) and systemic events (fever, chills, and

diaphoresis) occurring at any time during the study and within 2 weeks after the last dose of IP will be considered AEs of special interest (AESIs). If a subject develops fever, chills or abnormal sweating they will be instructed to contact the study team as soon as possible.

During clinic and telephone visits, according to the Schedule of Events (Section 2.2), a study team member complete a check list, which will be used for the solicited collection of specific AEs (adverse events of special interest) occurring since their previous study visit. These AEs include the following:

- Gastrointestinal events: nausea, vomiting, diarrhea, constipation, abdominal distention, abdominal pain/cramps, and flatulence
- Systemic events: fever, chills and diaphoresis

Additionally, all subjects will be instructed to write down any adverse events of special interest that they may be having on the Patient Diary.

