11.2. Event Assessment and Follow-up of Adverse Events

All AEs will be captured on the appropriate eCRF. Information to be collected includes event description, time of onset, investigator's assessment of severity, relationship to IP, and time of resolution/stabilization of the event. All AEs occurring while on study must be documented appropriately regardless of relationship. All AEs will be followed to adequate resolution or stabilization, as determined by the investigator.

Any medical condition that is present at the time that the participant is screened will be considered as baseline and not reported as an AE. However, if the study participant's pre-existing medical condition deteriorates at any time during the study, it will be recorded as an AE.

Changes in the severity of an AE will be documented to allow an assessment of the duration of the event at each level of severity. AEs characterized as intermittent require documentation of onset and duration of each episode.

The study team will record all AEs with start dates occurring any time after informed consent is obtained until 14 days after study treatment. At each study visit, the study team will ask about the occurrence of AEs since the last visit whether in the clinic or on the phone. Any SAEs considered to be related to study treatment that occur beyond 14 days after study treatment will also be reported.

Subjects who discontinue IP early will continue to be monitored for 14 days from last treatment for AEs, unless they withdraw consent or are lost to follow-up.

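### After Period 2 no AE contact is required at or after day 14 from the last dose, so the promised 14-day AE and AESI collection may end a few days early (minor)

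*Protocol*

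**What the plan says.** **The promise.** Protocol Section 11.2 sets the recording duty: "The study team will record all AEs with start dates occurring any time after informed consent is obtained until 14 days after study treatment". Section 7.1 does the same for AESIs (seven gastrointestinal and three systemic symptoms): those arising in the study or "within 2 weeks after the last dose of IP will be considered AEs of special interest (AESIs), and will be solicited". Section 10.2.6.2.1 sets a matching 14-day limit for reporting clinically relevant laboratory changes as AEs. Section 11.2 also has subjects who stop early monitored for 14 days from their last treatment.

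**The contacts.** Section 10.2.5 puts the last clinic visit (Visit 4) on Day 28 of Period 2. Under Section 10.2.4 the weekly calls run between clinic visits within a treatment period, so they do not continue past Visit 4. Section 10.2.5 covers what follows: "The Post-Treatment Period will last up to 14 days, wherein subjects will not receive any study drug", and then "During this time, subjects will be contacted by telephone for reporting of AEs". The Schedule of Events (Section 2.2) has a post-trial washout column at Day 42 (± 4).

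**How events are elicited.** At clinic and telephone contacts a team member completes a checklist, "which will be used for the solicited collection of specific AEs (adverse events of special interest) occurring since their previous study visit". Section 11.2 likewise says that "the study team will ask about the occurrence of AEs since the last visit whether in the clinic or on the phone".

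**Other routes.** Section 7.1 states that "additionally AEs of special interest will be captured in the Patient Diary", and Section 10.2.6.1 repeats it as an instruction: "Additionally, all subjects will be instructed to write down any adverse events of special interest that they may be having on the Patient Diary". Section 10.2.6.1 also tells subjects to contact the team promptly about fever, chills or abnormal sweating. Section 9.4 has the dosing record kept in the diary and returned to the site.

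**The concern.** Backward-looking questions cover time only up to the contact at which they are asked. To deliver a 14-day window, the last contact must fall on or after day 14. Section 10.2.5 does not require that. Its period has an upper limit of 14 days and no lower limit, and the contact may fall anywhere inside it.

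The incidence of treatment-emergent AEs and AESIs is a primary endpoint (Section 6.2.1.1) of the first study of SB-121 in humans (Section 5.3), and oral Sephadex has not been tested clinically before (Section 7.3). Events that begin after an early last call reach the database only if the subject volunteers them or a diary entry is retrieved. The instruction to contact the site covers the systemic symptoms, not the gastrointestinal ones. Section 10.2.1 treats participants' ability to report AEs as something to be assessed, so unprompted reporting is a weaker route here than asking.

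**Working it through.** **1. The plan's own figures.** Section 10.1 lists 14 + 28 + 14 + 28 + 14 = 98 days, matching its stated maximum duration. The nominal post-trial time point is Day 42 − Day 28 = 14 days after a Day 28 last dose. The nominal target is therefore right; the question is what the tolerance and the open wording allow.

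**2. What the text alone gives.** Section 10.2.5 yields no day count. It shows only that no contact is required at or after day 14.

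**3. Size, if Day 42 (± 4) is the AE call.** This is an inference: the table is broken in the extracted text, and the marks in that column cannot be confirmed. Inputs:

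- Call window: 42 − 4 = Day 38 to 42 + 4 = Day 46 (Section 2.2).
- Last dose: Day 28 if dosing ends as in Section 10.2.3 (1 + 27 doses); Day 30 if the synopsis figure of 30 Period 2 doses applies; Day 25 or 31 if dosing ends with Visit 4 at the edge of its ± 3 window.

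Unsolicited days = max(0, 14 − (call day − last-dose day)).

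| Last dose | Call Day 38 | Call Day 42 | Call Day 46 |
|---|---|---|---|
| Day 25 | 14 − 13 = 1 | 0 | 0 |
| Day 28 | 14 − 10 = 4 | 14 − 14 = 0 | 0 |
| Day 30 | 14 − 8 = 6 | 14 − 12 = 2 | 0 |
| Day 31 | 14 − 7 = 7 | 14 − 11 = 3 | 0 |

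For a Day 28 last dose, calls on Days 38, 39, 40 and 41 leave 4, 3, 2 and 1 days. Calls on Day 42 to 46 leave none.

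**4. Period 1 for comparison.** Footnote h of the Schedule starts Period 2 on Day 42 or up to 7 days later. Visit 3 is therefore 42 − 28 = 14 to 49 − 28 = 21 days after a Day 28 last dose, and staff then ask about the interval since the previous visit. There is no gap. If Period 1 dosing ran a little later, AE questioning would simply continue into Period 2.

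**5. Effect on the treatment contrast.** Sequences are randomized 1:1, so each treatment is the Period 2 treatment for about half the subjects. SAP Section 6.1 combines the periods by treatment. Any loss after Period 2 therefore falls on SB-121 and placebo about equally.

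**The case against.** The strongest reply is that the duty is already stated. Sections 7.1 and 11.2 require recording and solicitation through 14 days, and Section 10.2.5 does not limit the site to one call. A site that stopped at Day 38 would meet a visit window but not the duty, and a symmetric window around the correct nominal day is ordinary tolerance. This is fair, and it rules out reading the plan as providing no AE follow-up after Visit 4 or only a single call; the documents say neither. What stands is that no timing rule makes the site carry out the duty at the end of the window.

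Second, the day counts rest on an unlabelled column in a broken table. That is correct, so they are conditional. A reader might also take 4 days as a maximum; the documents do not support that, because the count moves with the last dose (1 to 7 days in the table above for a Day 38 call).

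Third, the backstops are real: the diary, the instruction on systemic symptoms, and Section 11.2's reporting of related serious events even beyond 14 days. In the preclinical work Sephadex cleared within 24 to 48 hours (Section 5.4.3), so days 11 to 14 may yield few product-related gastrointestinal events. These arguments reduce the importance of the point. They do not close the gap, because no diary return or review after Visit 4 is described.

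**Conclusion.** The point holds as a minor one, worth considering. The stated timing rules do not ensure the 14-day AE and AESI collection that the protocol promises after Period 2. That conclusion rests on the text of Sections 7.1, 10.2.4, 10.2.5, 10.2.6.1 and 11.2 and does not need the Schedule table.

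The size does need it. If the Day 42 column is the AE call, up to 4 of the 14 days go unsolicited after a Day 28 last dose, and more if dosing ends later. How many calls would fall early is unknown, so no average loss can be given.

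The consequence is a small possible understatement of absolute AE and AESI incidence after Period 2. A reader might infer a bias in favour of SB-121. The crossover does not support that, since both treatments lose about the same follow-up, and the safety analyses are descriptive with no formal comparison (Protocol Section 13.1.4; SAP Section 6.7.2).

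**What to change.** - Set the final AE/AESI call at the actual last dose + 14 days, with a window of 0/+4 days. For a Day 28 last dose this is 28 + 14 = Day 42 to 28 + 18 = Day 46.
- At that call, have the checklist and a review of the Patient Diary cover the whole interval since Visit 4.
- Use the same anchor for subjects who stop treatment early.
- In the synopsis duration entry and Sections 10.1 and 10.2.5, replace the 14-day upper limit with at least 14 days, ending with the final AE call. In Section 7.5, let the study end at that call when it falls later than 14 days.

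The cost is small. No contact is needed beyond the telephone follow-up already planned. For a Day 28 last dose the latest call date stays at Day 46; it moves later only if dosing ends later (30 + 18 = Day 48 for a Day 30 last dose). For a Day 28 last dose the site loses 4 of its 9 call dates (Days 38 to 41), and subjects who would have been called then finish follow-up between 1 day (41 to 42) and 8 days (38 to 46) later.
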